### 5.3 Schematic diagram

The study schematic diagram for PS0016 is presented in [Figure 5–1](#).

**Figure 5–1: Schematic diagram of PS0016**

PASI= Psoriasis Area and Severity Index; SFU=Safety Follow-Up

From Week 20 through Week 28, subjects who were previously PASI25 responders but subsequently relapse (defined as returning to less than PASI25 response) will undergo the study assessments for that visit (ie, Week 20, Week 24, or Week 28) before receiving their first dose of study treatment in the extension study at Week 20, Week 24, or Week 28. Subjects eligible for the extension study must have the assessments for SFU conducted prior to entering the extension study. Subjects who have not achieved a PASI25 response at any visit prior to Week 20 will not be eligible to enter the extension study. All subjects not enrolling in the extension study will continue in PS0016 until the SFU Visit at Week 36.

### 5.4 Rationale for study design and selection of dose

PS0016 is a Phase 2a, a multicenter, randomized, subject-blind, investigator-blind study to evaluate the PD, PK, and safety of bimekizumab in adult subjects with moderate to severe chronic plaque psoriasis Treatment Period (28 weeks) and a SFU Period (20 weeks after the last dose of study medication).

The inclusion criteria are designed to ensure all subjects have moderate to severe disease activity. Some exclusion criteria are intended to eliminate subjects who may present an unacceptable safety risk were they to participate in this investigational study program. The full list of inclusion and exclusion criteria is provided in [Section 6](#).

The study will evaluate 2 regimens of bimekizumab to understand the time course of PASI response following sc administration of bimekizumab:

- Treatment arm A: Bimekizumab 320mg at Week 0 and 4 administered sc, placebo administered at Week 16
- Treatment arm B: Bimekizumab 320mg at Weeks 0, 4, and 16 administered sc

The dose level and regimens were chosen based on the efficacy and safety data from the 3 completed clinical studies of bimekizumab (UP0008, RA0124, and PA0007). The selected dosage regimens will in maximum likelihood provide information to evaluate the time-course of PASI response following administration of bimekizumab treatment in this patient population.

All the subjects in the study will receive 320mg of bimekizumab as a sc injection at Baseline and Week 4. Based on our current understanding of PKPD of bimekizumab this will enable maximum PASI response in the subjects. Subjects will then be administered either placebo (Treatment arm A) or 320mg of bimekizumab at Week 16 (Treatment arm B), in order to evaluate the change in time course of PASI response. The proposed doses are expected to be safe since doses greater than 320mg (ie, up to 640mg) have been previously tested, via intravenous administration, in the development of bimekizumab and were found to be safe and well tolerated.

## 6 SELECTION AND WITHDRAWAL OF SUBJECTS

### 6.1 Inclusion criteria

To be eligible to participate in this study, all of the following criteria must be met at Screening and be re-confirmed at the Baseline Visit. (Note: the 1 exception relates to the laboratory tests performed at Baseline Visit, from which only the pregnancy test result needs to be known prior to administration of study medication.)

- 1a. An Institutional Review Board (IRB)/Independent Ethics Committee (IEC) approved written Informed Consent Form is signed and dated by the subject.
- 2a. Subject is considered reliable and capable of adhering to the protocol (eg, able to understand and complete diaries), visit schedule, or medication intake according to the judgment of the Investigator.
3. Subject is at least 18 years of age and less than or equal to 70.
4. Subject has had chronic plaque psoriasis for at least 6 months prior to Screening.
5. Subject has PASI  $\geq 12$  and BSA  $\geq 10\%$  and IGA score  $\geq 3$  on a 5-point scale.
6. Subject is a candidate for systemic psoriasis therapy and/or phototherapy and/or chemophototherapy.
7. **Female** subjects must be postmenopausal (at least 1 year; to be confirmed hormonally as part of the Screening process, if less than 2 years since last menstrual period), permanently sterilized (eg, tubal occlusion, hysterectomy, bilateral salpingectomy) or, if of childbearing potential, must be willing to use a highly effective method of contraception up until 20 weeks after last administration of study drug, and have a negative pregnancy test at Screening and immediately prior to first dose. The following methods are considered highly effective when used consistently and correctly.

- Combined (estrogen and progestogen) hormonal contraception associated with inhibition of ovulation (oral, intravaginal or transdermal)
- Progestogen-only hormonal contraception associated with inhibition of ovulation (oral, injectable, implantable)
- Intrauterine device (IUD)
- Intrauterine hormone-releasing system (IUS)
- Bilateral tubal occlusion
- Vasectomized partner (where postvasectomy testing had demonstrated sperm clearance).
- Sexual abstinence if it is in accordance with a subject's preferred and common lifestyle. Subjects who use abstinence as a form of birth control must agree to abstain from heterosexual intercourse until 20 weeks after the last dose of study medication. Study personnel must confirm the continued use of abstinence is still in accordance with the subject's lifestyle at regular intervals during the study.

**Male** subjects with a partner of childbearing potential must be willing to use a condom when sexually active, up till 20 weeks after the last administration of study medication (anticipated 5 half-lives).

8. Subject agrees to not increase their usual sun exposure during the course of the study and to use ultraviolet A/ultraviolet B (UVA/UVB) sunscreens.

## 6.2 Exclusion criteria

Subjects are not permitted to enroll in the study if any of the following criteria is met:

1. Female subjects who are breastfeeding, pregnant, or plan to become pregnant during the study or within 20 weeks following last dose of study drug. Male subjects who are planning a partner pregnancy during the study or within 20 weeks following the last dose.
2. Subjects previously participating in a bimekizumab clinical trial.
3. Subjects participating in another study of a medication or a medical device under investigation within the last 3 months or at least 5 half-lives, whichever is greater, or is currently participating in another study of a medication or medical device under investigation.
4. Subjects with a known hypersensitivity to any excipients of bimekizumab.
- 5a. Subjects with erythrodermic, guttate, pustular form of psoriasis, or drug-induced psoriasis.
6. Subjects with a history of chronic or recurrent infections, or a serious or life-threatening infection within the 6 months prior to the Baseline Visit (including herpes zoster). Subjects with a high risk of infection in the Investigator's opinion (eg, subjects with leg ulcers, indwelling urinary catheter, persistent or recurrent chest infections, prior prosthetic joint infection at any time, subjects who are permanently bedridden or wheelchair assisted).
7. Subject has any current sign or symptom that may indicate an active infection (except for common cold), or has had an infection requiring systemic antibiotics within 2 weeks of baseline.

8. Subjects with concurrent acute or chronic viral hepatitis B or C or human immunodeficiency virus (HIV) infection. Subjects who have evidence of, or tested positive for hepatitis B or hepatitis C are excluded. A positive test for the hepatitis B virus (HBV) is defined as: 1) positive for hepatitis B surface antigen (HBsAg+); or, 2) positive for anti-hepatitis B core antibody (HBcAb+). A positive test for the hepatitis C virus (HCV) is defined as: 1) positive for hepatitis C antibody (anti-HCV Ab), and 2) positive via a confirmatory test for HCV (for example, HCV polymerase chain reaction).
9. Subjects with known history of or current clinically active infection with *Histoplasma*, *Coccidioides*, *Paracoccidioides*, *Pneumocystis*, nontuberculous mycobacteria, *Blastomyces*, or *Aspergillus* or current active Candidiasis (local or systemic).
10. Subjects receiving any live (includes attenuated) vaccination within the 8 weeks prior to Baseline (eg, inactivated influenza and pneumococcal vaccines are allowed but nasal influenza vaccination is not permitted). Live vaccines are not allowed during the study or for 20 weeks after the last dose of study drug.
11. Subjects receiving Bacillus Calmette-Guerin (BCG) vaccinations within 1 year prior to study drug administration.
12. Subjects with a history of a lymphoproliferative disorder including lymphoma or current signs and symptoms suggestive of lymphoproliferative disease.
13. Subjects with primary immunosuppressive conditions, including subjects who are taking immunosuppressive therapy following an organ transplants.
14. Subjects with known TB infection, at high risk of acquiring TB infection, with latent TB infection (LTBI), or current or history of NTMB infection (refer to [Section 12.6.1](#) for details on determining full TB exclusion criteria).
15. Subjects who have had a splenectomy.
16. Subjects with concurrent malignancy or history of malignancy (including surgically resected uterine/cervical carcinoma-in-situ) during the past 5 years, will be excluded, with the following exceptions, that may be included.
  - a.  $\leq 3$  excised or ablated, basal cell carcinomas of the skin
  - b. One squamous cell carcinoma of the skin (stage T1 maximum) successfully excised, or ablated only (other treatments, ie, chemotherapy, do not apply), with no signs of recurrence or metastases for more than 2 years prior to Screening
  - c. Actinic keratosis(-es)
  - d. Squamous cell carcinoma-in-situ of the skin successfully excised, or ablated, more than 6 months prior to Screening
17. Subjects having had major surgery (including joint surgery) within the 6 months prior to Screening, or planned surgery within 6 month after entering the study.
18. Subjects with a current or recent history, as determined by the Investigator, of severe, progressive, and/or uncontrolled renal, hepatic, hematological, endocrine, pulmonary, cardiac (eg, congestive heart failure, New York Heart Association [NYHA] Grade 3 and 4),

gastrointestinal (GI) (note: subjects with active peptic ulcer disease are excluded; subjects with a history of peptic ulcer disease are allowed), or neurological disease.

19. Subject has a history of uncompensated heart failure, fluid overload, or myocardial infarction, or evidence of new onset ischemic heart disease or in the opinion of the Investigator other serious cardiac disease, within 12 weeks prior to Baseline.
- 20a. Subject has >2x upper limit of normal (ULN) of any of the following: alanine aminotransferase (ALT), aspartate aminotransferase (AST), alkaline phosphatase (ALP), or >ULN total bilirubin ( $\geq 1.5 \times \text{ULN}$  total bilirubin if known Gilbert's syndrome). If subject has elevations only in total bilirubin that are >ULN and <1.5xULN, fractionate bilirubin to identify possible undiagnosed Gilbert's syndrome (ie, direct bilirubin <35%).

Tests that result in ALT, AST, or ALP up to 25% above the exclusion limit may be repeated once for confirmation during the Screening Period. Upon retesting, subjects whose ALT, AST, or ALP remain above the thresholds defined above, should not be randomized.

For randomized subjects with a baseline result >ULN for ALT, AST, ALP, or total bilirubin, a baseline diagnosis and/or the cause of any clinically meaningful elevation must be understood and recorded in the Case Report form (CRF).

If subject has >ULN ALT, AST, or ALP that does not meet the exclusion limit at screening, repeat the tests, if possible, prior to dosing to ensure there is no further ongoing clinically relevant increase. In case of a clinically relevant increase, inclusion of the subject must be discussed with the Medical Monitor.
21. Subjects with clinically significant laboratory abnormalities (eg, creatinine >1.5xULN, neutropenia <1.5x10^9/L, hemoglobin <8.5g/dL, lymphocytes <1.0 x10^9/L, platelets <100 x10^9/L). Individual screening tests for which the results are in error, borderline, or indeterminate for inclusion in the study, can be repeated once for confirmation during the screening period if they are within 25% of the exclusion limit. Upon retesting, subjects whose results remain outside this threshold should not be randomized.
22. Subjects with any other condition which, in the Investigator's judgment, would make the subject unsuitable for inclusion in the study.
23. Subjects have been exposed to more than 1 biological response modifier (limited to anti-TNF or IL-12/-23) or have received any biologic response modifier during the three months prior to the Baseline Visit. The list of prohibited medications is presented in [Section 7.8.2](#).
24. Subjects have received previous treatment with any anti-IL-17 therapy for the treatment of psoriasis or psoriatic arthritis.
- 25a. Subjects with a diagnosis of inflammatory conditions other than psoriasis or psoriatic arthritis, including but not limited to rheumatoid arthritis, sarcoidosis, or systemic lupus erythematosus. Subjects with a diagnosis of Crohn's disease or ulcerative colitis are allowed as long as they have no active symptomatic disease at Screening or Baseline.
26. Subjects taking psoriatic arthritis medications other than nonsteroidal anti-inflammatory drugs (NSAIDs) or analgesics. Subjects already receiving an established NSAID regimen (at least 8 weeks prior to Baseline) and who have been on a stable dose for at least 4 weeks prior to Baseline may continue their use during the study.

27. Subject has a history of chronic alcohol or drug abuse within the previous 6 months.
28. Subject has 12-lead ECG with changes considered to be clinically significant upon medical review (eg, QT corrected for heart rate [QTc] using Fridericia's correction [QTcF] >450ms, bundle branch block, evidence of myocardial ischemia).
- 29a. Presence of significant uncontrolled neuropsychiatric disorder, active suicidal ideation, or positive suicide behavior using the "Baseline" version of the C-SSRS and the HADS with either of the following criteria:
  - Subject has a lifetime history of suicide attempt (including an actual attempt, interrupted attempt, or aborted attempt), or has suicidal ideation in the past 6 months as indicated by a positive response ("Yes") to either Question 4 or Question 5 of the "Screening/Baseline" version of the C-SSRS at Screening.
  - HADS Depression score >10 or Anxiety score  $\geq$ 15
30. Subject is an Investigator site worker directly affiliated with this study and/or an immediate family member. Immediate family is defined as a spouse, parent, child or sibling, whether biological or legally adopted.
31. Subject is a UCB employee or employee of third-party organizations involved in the study.
32. Subjects who have been admitted to a mental hospital or other institution by an order of the court

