**Table 5–1: Schedule of assessments**

Visit a / Week  Protocol activity	Screening b	Baseline	Treatment Period (Time after the first dose)							Wk 36 EWD/ SFU c
			Wk 2	Wk 4	Wk 8	Wk 12	Wk 16	Wk 20	Wk 24	

BSA=body surface area; C-SSRS= Columbia Suicide Severity Rating Scale; ECG=electrocardiogram; EWD=Early Withdrawal; FSH=follicle stimulating hormone; HADS=Hospital Anxiety and Depression Scale; HIV=human immunodeficiency virus; IGA=Investigator’s Global Assessment; IGRA=interferon-gamma release assay; IXRS=interactive voice or web response system; PASI=Psoriasis Area and Severity Index; PK=pharmacokinetics; SFU=Safety Follow-Up; TB=tuberculosis; Wk=week

a Visit windows of ±3 days from the first dose at all visits except SFU. Safety Follow-Up Visit window is -3 and +7 days.

b The Screening Period will last up to a total of 4 weeks.

c The SFU Visit will occur 20 weeks after the last dose.

d A separate Informed Consent Form is required to be completed for the extension study.

e Ensure no significant changes in medical history.

f Vital signs (blood pressures, pulse rate, and temperature) are to be measured prior to blood sampling, and prior to dosing, where applicable.

g The FSH test should only be performed on postmenopausal females who have been postmenopausal for ≥1 year and last menstrual cycle occurred <2 years ago.

h At Baseline and Weeks 4 and 16, to be performed predose.

i Pregnancy testing will be serum testing at Screening and SFU. The pregnancy test will be urine at all other visits. If the subject is entering the extension study, a urine pregnancy test will be performed at SFU.

j Subjects who have evidence of or test positive for hepatitis B by any of the following criteria: 1) positive for hepatitis B surface antigen (HBsAg+); 2) positive for anti-hepatitis B core antibody (HBcAb+) and negative for anti-hepatitis B surface antibody (HBsAb–) are excluded; a positive test for HCV is defined as: 1) positive for hepatitis C antibody (anti-HCV Ab), and 2) positive via a confirmatory test for HCV (for example, HCV polymerase chain reaction) are also excluded.

k A chest x-ray must be performed at Screening or must occur within 3 months prior to Screening and results must be available at Baseline. MMR is not acceptable.

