**Table 7-1: Prohibited psoriasis medications**

Drug	Exclusion criteria prior to Baseline Visit
Systemic retinoids	12 weeks
Systemic treatment (non-biological): systemic immunosuppressant agents (eg, methotrexate, cyclosporine, azathioprine, thioguanine) systemic fumarate systemic corticosteroids phototherapy or chemophototherapy	8 weeks for methotrexate, azathioprine, and cyclosporine 4 weeks for everything other than methotrexate, azathioprine, and cyclosporine
Anti-TNFs: infliximab (including biosimilar), golimumab etanercept (including biosimilar) certolizumab pegol adalimumab (including biosimilar)	4 weeks for etanercept 12 weeks for everything other than etanercept
Other biologics and other systemic therapies: apremilast ustekinumab	12 weeks for apremilast 24 weeks for ustekinumab
Anti-IL-17 therapy	Any previous exposure excluded

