## 8 STUDY PROCEDURES BY VISIT

Table 5–1 (schedule of study assessments) provides a general overview of study assessments. A list of procedures to be completed at each visit is described below.

- Visit windows of  $\pm 3$  days on either side of the scheduled dosing are permitted; however, the Investigator should try to keep the subjects on the original dosing schedule. The window of  $\pm 3$  days is relative to Baseline and applicable for all subsequent visits. Changes to the dosing schedule outside of the 3-day window must be discussed with the Medical Monitor.
- For the Safety Follow-Up Visit (20 weeks after the last dose), the visit should occur no more than 3 days prior to the scheduled visit date and within 7 days after the scheduled visit date (-3 days/+7 days).

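### Two eligibility rules conflict in the current protocol: hepatitis B core antibody (criterion 8 against Table 5-1 footnote j) and etanercept washout (criterion 23 against Table 7-1)

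*Protocol*

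**What the plan says.** **Hepatitis B.** Protocol Section 6.2, criterion 8, counts a subject as hepatitis B positive if "1) positive for hepatitis B surface antigen (HBsAg+); or, 2) positive for anti-hepatitis B core antibody (HBcAb" positive). Surface antibody is not mentioned. Footnote j to Table 5-1, which belongs to the hepatitis testing row, also excludes on surface antigen, but gives its second pattern as "positive for anti-hepatitis B core antibody (HBcAb+) and negative for anti-hepatitis B surface antibody".

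**Etanercept.** Criterion 23 of Section 6.2 contains two bars. The first excludes subjects exposed to more than one biologic of the anti-TNF or IL-12/-23 classes. The second excludes subjects who "have received any biologic response modifier during the three months prior to the Baseline Visit". The criterion then directs the reader to Section 7.8.2: "The list of prohibited medications is presented in" that section. Table 7-1 there, in a column headed "Exclusion criteria prior to Baseline Visit", gives the anti-TNF periods as "4 weeks for etanercept 12 weeks for everything other than etanercept".

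**How the texts rank.** Section 6.2 opens with "Subjects are not permitted to enroll in the study if any of the following criteria is met", so a single criterion is enough to exclude. Section 8 says that Table 5-1 "provides a general overview of study assessments".

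**The concern.** A site that screens from footnote j could pass a subject whom criterion 8 excludes, and a site that applies the Table 7-1 washout could pass a subject whom criterion 23 excludes. Each of the two places reads as an eligibility rule: footnote j says which subjects are excluded, and the Table 7-1 column is titled as exclusion criteria.

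The hepatitis B rule is a safety exclusion for an immunomodulating antibody. The conflict can arise in practice, because SAP Table 11-1 lists anti-HBs in the serology panel, so the result that footnote j turns on is planned to be available. The etanercept conflict decides whether a recently treated subject may be enrolled or has been enrolled in breach of a criterion.

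**Working it through.** No figure in the plan depends on these rules, so there is none to reproduce. The check is to find which subjects each pair of texts classifies differently.

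**Hepatitis B, by serology pattern**

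| HBsAg | HBcAb | HBsAb | Criterion 8 | Footnote j |
|---|---|---|---|---|
| + | any | any | excluded | excluded |
| - | + | - | excluded | excluded |
| - | + | + | excluded | not listed |
| - | - | any | not excluded | not listed |

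Only the third row differs.

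**Etanercept, by time since last dose**

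Inputs: three months (criterion 23); 4 weeks for etanercept, 12 weeks for other anti-TNFs and 24 weeks for ustekinumab (Table 7-1). The protocol does not convert three months to days. I take it as 12 weeks = 84 days, or as calendar months = 89 to 92 days.

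Disputed window = three months minus 4 weeks (28 days):
- at 84 days: 84 - 28 = 56 days (8.0 weeks)
- at 89 days: 89 - 28 = 61 days
- at 92 days: 92 - 28 = 64 days (9.1 weeks)

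A last dose within 4 weeks of Baseline fails both texts, and one more than three months before passes both. Between those points, criterion 23 excludes and Table 7-1 does not.

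The first bar in criterion 23 narrows the group. A subject who has had etanercept and a second anti-TNF or IL-12/-23 biologic is excluded whatever the timing. The dispute is therefore confined to subjects whose only such biologic was etanercept.

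**Is this a general mismatch between criterion 23 and Table 7-1?**
- Other anti-TNFs, 12 weeks = 84 days: 84 - 84 = 0, 89 - 84 = 5 and 92 - 84 = 8 days. Trivial.
- Ustekinumab, 24 weeks = 168 days: the table is longer by 168 - 92 = 76 to 168 - 84 = 84 days. The two texts then act as cumulative minimums and do not conflict.
- Etanercept is the exception. Its table entry is shorter than the catch-all and so has no effect as written, although the table deliberately sets it apart from the other anti-TNFs.

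**Which etanercept period was meant?** The conflicting statements are all in the current protocol body, so the amendment log is used here only as evidence of intent. Amendment 1 lists clarification of the etanercept exclusion among its purposes, and its Change #28 introduced the 4-week entry. Its changes to Section 6.2 (#17 to #20) touch criteria 5, 20, 25 and 29, not 23. That points to 4 weeks as the intended rule and to a conforming edit that was missed.

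**The case against.** The strongest reply is that the documents already settle which text wins. Section 6.2 is cumulative, Table 5-1 is only an overview, and Sections 8.1 and 8.2 require the inclusion and exclusion criteria to be assessed at Screening and confirmed at Baseline. A site that does this excludes both groups. That stands, and it is why the point is minor. It does not make the other texts harmless: criterion 23 itself sends the reader to the table with the shorter period, and the footnote sits on the row that orders the test.

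A reader might go further in four ways that the documents do not support.

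- *That footnote j permits HBcAb-positive, HBsAb-positive subjects to enrol.* It does not say so. It lists patterns that are excluded, without the word only, and a subject who is clear of the footnote is still caught by criterion 8.
- *That every subject with etanercept in the window is in dispute.* The bar on more than one prior biologic removes those with a second anti-TNF or IL-12/-23 agent.
- *That eligibility deviations have no rule to be classified against.* SAP Section 3.4 does place eligibility deviations among the important ones, but it assigns the criteria for identifying them to a protocol deviation specifications document; Protocol Section 14.4 likewise defers to a separate document. That document is not available here, so its content cannot be called missing.
- *That the efficacy results are affected.* The FAS in SAP Section 3.5.4 has no deviation condition. The PPS in Section 3.5.5 drops only subjects whose deviations affect the measurement, and past hepatitis B serology would not obviously affect a PASI score. The sample size came from PKPD simulation.

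**Conclusion.** The two conflicts are real and are in current protocol text. Severity is minor. The hepatitis B texts differ for one serology pattern. The etanercept texts differ for subjects with etanercept as their sole prior anti-TNF or IL-12/-23 biologic and a last dose in a window of 56 to 64 days; the range rests on reading three months as 12 weeks or as calendar months. The documents give no count of subjects in either group. The consequence is limited to consistent eligibility screening, including one safety exclusion. The preference for 4 weeks rests on Amendment 1 as evidence of intent; until criterion 23 is edited, its three months governs.

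**What to change.** - **Table 5-1 footnote j:** delete the condition that surface antibody be negative, so that it matches criterion 8.
- **Criterion 23:** keep the three-month catch-all, because Table 7-1 covers psoriasis medications and does not list every biologic. Add: *except etanercept, 4 weeks; longer drug-specific periods in Table 7-1 also apply*.
- **Protocol deviation specifications document:** use the same rules as the corrected Section 6.2.
- **Editorial, in passing:** Section 12.5 cites exclusion criterion 7 for hepatitis and HIV testing; it should cite criterion 8.

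The cost is wording in the next protocol amendment, with no extra subjects, visits or procedures. If enrolment has closed, the same resolution can be recorded in the deviation specifications before unblinding.
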